1. To compare rates of all-cause mortality in the 180 days following enrolment for an episode of high risk diarrhea without dysentery among children 2 to 23 months of age living in low resource settings who are randomized to receive a 3-day course of azithromycin or placebo.
2. To compare the change in linear growth (Δ LAZ) in the 90 days following an episode of high risk diarrhea without dysentery among children 2 to 23 months of age living in low resource settings who are randomized to receive a 3-day course of azithromycin or placebo.

3.2 Secondary Objectives:

Following an episode of high risk diarrhea without dysentery among children 2 to 23 months of age living in low resource settings who are randomized to receive a 3-day course of azithromycin or placebo, comparison by trial allocation arm of:

1. proportion of children with at least one hospitalization in the 90 days following enrolment
2. proportion of children with at least one hospitalization or who died in the 90 days following enrolment.
3. proportion of children with at least one hospitalization or who died in the initial 10 days following enrolment.
4. change in weight-for-length Z-score (Δ WLZ) in the 90 days following enrolment.
5. change in weight-for-length Z-score (Δ WAZ) in the 90 days following enrolment.
6. change in mid-upper arm circumference (Δ MUAC) in the 90 days following enrolment.
7. Prevalence of azithromycin resistant *E.coli* at baseline among a random subsample of enrolled participants.
8. Prevalence of azithromycin resistant *E.coli* and azithromycin resistant *S. pneumoniae* at D90 and D180 among a random subsample of enrolled participants and their household contacts.
9. Describe cause-specific mortality rates (as determined by verbal autopsy) in the 90 days following enrolment.

3.3 Trial implementation process outcomes:

By trial allocation arm:

1. Describe baseline characteristics
2. Describe dose compliance

3. Proportion of children with a documented serious adverse event in the initial 10 days following enrolment
4. Describe protocol deviations

By country of enrolment:

5. Describe baseline characteristics by country of enrolment
6. Describe dose compliance by country of enrolment

4 General approach to data analysis

4.1 Intention to treat (ITT) analysis:

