4.6 Adjusting for baseline measure in change from baseline outcomes

Primary Objective 2 is change from baseline in length-for-age Z-score. Change from baseline outcomes will be adjusted for the baseline value in order to avoid the phenomenon of regression to the mean. In an analysis of covariance (ANCOVA) framework, this can be achieved by including baseline metric in the model. Identically, the same adjustment is achieved by including participant level covariates as random effects in a mixed effects model. This accounts for the clustering of length-for-age and weight-for-length across the two timepoints (enrolment and day 90) within each enrolled participant.

5 Hypotheses to be tested

Primary Objective 1 – 180 day mortality:

Null hypothesis: Among children 2-23 months of age with moderate to severe diarrhea, 180 day mortality is independent of treatment allocation to placebo or to a 3-day course of oral azithromycin.

Alternative hypothesis: Among children 2-23 months of age with moderate to severe diarrhea, 180 day mortality is not independent of exposure i.e. those allocated to receive a 3-day course of oral azithromycin compared to those allocated to receive oral placebo..

Primary Objective 2 – Change in Length-for-age z-score:

Null hypothesis: Among children 2-23 months of age with moderate to severe diarrhea, the mean change from baseline in length-for-age z-score (ΔLAZ) over the 90 day follow-up period is independent of treatment allocation to placebo or to a 3-day course of oral azithromycin.

Alternative hypothesis: Among children 2-23 months of age with moderate to severe diarrhea, the mean change from baseline in ΔLAZ over the 90 day follow-up period is not independent of exposure i.e. among those treated with a 3-day course of oral azithromycin than those treated with a placebo preparation.

Secondary objective 1 – Hospitalization by day 90

Null hypothesis: Among children 2 to 23 months of age with moderate to severe diarrhea, the proportion of children hospitalized by day 90 after enrolment, is independent of treatment allocation to placebo or to a 3-day course of oral azithromycin.

Alternative hypothesis: Among children 2 to 23 months of age with moderate to severe diarrhea, the proportion of children hospitalized by day 90 after enrolment, is not equal in the placebo arm and the arm receiving 3-day course of oral azithromycin.

Secondary objective 2 – Hospitalization or death by day 90

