Null hypothesis: Among children 2 to 23 months of age with moderate to severe diarrhea, the proportion of children hospitalized or dying by D90 after enrolment, is independent of treatment allocation to placebo or to a 3-day course of oral azithromycin.

Alternative hypothesis: Among children 2 to 23 months of age with moderate to severe diarrhea, the proportion of children hospitalized or dying by D90 after enrolment, is not equal in the placebo arm and the arm receiving 3-day course of oral azithromycin.

Secondary objective 3 – Hospitalization or death by day 10

Null hypothesis: Among children 2 to 23 months of age with moderate to severe diarrhea, the proportion of children hospitalized or dying by day 10 after enrolment, is independent of treatment allocation to placebo or to a 3-day course of oral azithromycin.

Alternative hypothesis: Among children 2 to 23 months of age with moderate to severe diarrhea, the proportion of children hospitalized or dying by day 10 after enrolment, is not equal in the placebo arm and the arm receiving 3-day course of oral azithromycin.

Secondary Objective 4, 5 & 6 - Acute wasting:

Null hypothesis: Among children 2-23 months of age with moderate to severe diarrhea, the mean change from baseline in weight-for-length z-score (ΔWLZ), weight-for-age z-score (ΔWAZ) and mid-upper arm circumference ($\Delta MUAC$) over the 90 day follow-up period is independent of treatment allocation to placebo or to a 3-day course of oral azithromycin.

Alternative hypothesis: Among children 2-23 months of age with moderate to severe diarrhea, the mean change from baseline in weight-for-length z-score (ΔWLZ), weight-for-age z-score (ΔWAZ) and mid-upper arm circumference ($\Delta MUAC$) over the 90 day follow-up period is not independent of treatment allocation to placebo or to a 3-day course of oral azithromycin.

Secondary objective 7: descriptive report of prevalence of azithromycin resistant *E.coli* from stools provided at baseline by a sub sample of children enrolled into the trial.

Secondary Objective 8- Antibiotic resistance:

Null hypothesis: Among the subset of children 2-23 months of age with moderate to severe diarrhea selected to be in the AMR sub-study, the prevalence of resistance to azithromycin in *E. coli* and *S. pneumoniae* is greater than or equal to 10% points higher in the group randomized to a 3-day course of oral azithromycin than those randomized to placebo.

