Definition of 180 day Mortality: Death due to any cause occurring ≤ 180 days post-randomization. The day of enrolment in the trial is termed “Study Day 1” therefore 180 days post enrollment is Study Day 181. All deaths or censoring events occurring from enrolment and up to and including Study Day 181 will be included in the primary analysis of the mortality outcome. Deaths and censoring events occurring on or after Study Day 182 (181 days since enrolment) will not be included in the analysis. Other mortality outcomes such as death by day 10 (part of Secondary Outcome 4) and day 90 (part of Secondary Objective 6) will also be defined on basis that day of enrolment is termed “Study Day 1”, making these outcomes on Study Day 11 and 91 respectively.

Date of death:

The date of death may be extracted *in ordered preference* from:

1. Death certificate
2. Hospital or clinic record
3. Caregiver other official written record
4. Caregiver recall

Note that forms do not currently record source of death date. Local SOP's should outline the above ordered preference.

Date of death currently appears on three forms (“Form 08-Vital Status”; “Form 11-SAE”; and on the verbal autopsy form). In cases of conflict among forms, the date appearing on Form 08-Vital Status should be prioritized over other forms.

7.2 Length-for-age Z-score (LAZ):

Length for age will be determined from age, sex, and length information at the date of enrolment (day 1) and date of D 90visit (day 91 up to day 101) of participant age, using the macro developed by the WHO using the WHO 2006 multi-centre growth standard. The LAZ values will be rounded to two decimal points.

7.3 Weight-for-age Z-score (WAZ):

Weight for age will be determined from age, sex, and weight information at the date of enrolment (day 1) and date of final visit (day 91 up to day 101) of participant age, using the macro developed by the WHO using the WHO 2006 multi-centre growth standard. The WAZ values will be rounded to two decimal points.

7.3 Weight-for-length Z-score (WLZ):

Weight for length will be determined from age, sex, length and weight information at the date of enrolment (day 1) and date of final visit (day 91 up to day 101) of participant age, using the macro developed by the WHO using the WHO 2006 multi-centre growth standard. The WLZ values will be rounded to two decimal points.

7.4 Hospitalization:

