9.3 Analysis of secondary objectives 1, 2 and 3 - Hospitalization

Following an episode of high risk diarrhea without dysentery among children 2 to 23 months of age living in low resource settings who are randomized to receive a 3-day course of azithromycin or placebo, comparison by trial allocation arm of:

1. proportion of children hospitalized or died in the initial 10 days following enrolment.
2. proportion of children hospitalized in the 90 days following enrolment.
3. proportion of children hospitalized or died in the 90 days following enrolment.

Primary event considered will be the first episode of hospitalization per child. Hospitalization rates will be reported by country to understand heterogeneity across sites. Risk ratio will be estimated from a model including trial allocation and country of enrollment. Adjusted analysis will include effect modifying covariates, and sensitivity analysis will include unbalanced potential confounders by trial arm.

Hospitalization data are available as binary outcomes only, and date of hospitalization is missing for all events after 10 days of follow-up. Time to event analysis is not possible for the hospitalization outcome.

Since likelihood of hospitalization may cluster by clinic, the following log-binomial mixed effects model is proposed:

$$\log \Pr(Y_i = 1) = \beta_{0c} + \beta_1 C_i + \beta_2 Z_i \times 1_{\{t>t_0\}} + \varepsilon_i \quad - \text{Model 6}$$

Where

$$Y_i = \begin{cases} 1 & \text{hospitalized at least once by day 180} \\ 0 & \text{not hospitalized} \end{cases}$$

Under this definition we are accounting for clustering at clinic level. The b term is a random effects for the c^{th} clinic, and take account of the variance due to clustering within clinic.

The term $\beta_1 C_i$ is the fixed effect of country, with C_i representing the country of enrolment for child i .

The term $\beta_2 Z_i$ is the fixed effect of azithromycin, with Z_i representing the treatment allocation for child i where

$$Z_i = \begin{cases} 1 & \text{azithromycin} \\ 0 & \text{placebo} \end{cases}$$

The term ε_{ij} is the variance component due to random error for child i at time j .

Adjusted analysis will include individual level effect modifiers, thus:

$$\log \Pr(Y_i = 1) = \beta_{0c} + \beta_1 C_i + \beta_2 Z_i \times 1_{\{t>t_0\}} + \beta_{3X} \mathbf{X}_{ij} + \varepsilon_i \quad - \text{Model 7}$$

Where \mathbf{X}_{ij} is the vector of effect-modifying covariates of child i at time j :

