Figure 1. Participant flow in CONSORT recommended format (Lancet 2001; 357: 1193)

ABCD Consort Flow Diagram

Tables

Table 1. Participant characteristics at enrolment by trial allocation arm

Variable	Placebo	Azithromycin
Number of participants	xxx	xxx
Mean (SD) age, months	xx.x (xx.x)	xx.x (xx.x)
Proportion male, %	xx.x%	xx.x%
Mean (SD) weight, kg	xx.x (xx.x)	xx.x (xx.x)
Mean (SD) length, cm	xx.x (xx.x)	xx.x (xx.x)
Mean (SD) MUAC, cm	xx.x (xx.x)	xx.x (xx.x)
Mean (SD) LAZ, z-score units	xx.x (xx.x)	xx.x (xx.x)
Mean (SD) WLZ, z-score units	xx.xx (xx.xx)	xx.xx (xx.xx)
Prevalence of moderate stunting (-3.0<LAZ≤-2.0), %	xx.xx (xx.xx)	xx.xx (xx.xx)
Prevalence of severe stunting (LAZ≤-3.0), %	xx.xx (xx.xx)	xx.xx (xx.xx)
Prevalence of moderate wasting (-3.0<WLZ≤-2.0), %	xx.xx (xx.xx)	xx.xx (xx.xx)
Prevalence of some or severe dehydration, %	xx.xx (xx.xx)	xx.xx (xx.xx)
Mean (SD) maternal age, years	xx.x (xx.x)	xx.x (xx.x)
Mean (SD) maternal height, cm	xx.x (xx.x)	xx.x (xx.x)
Mean (SD) maternal weight, kg	xx.x (xx.x)	xx.x (xx.x)
Mean (SD) maternal BMI, kg / m ²	xx.x (xx.x)	xx.x (xx.x)
Mean (SD) maternal MUAC, cm	xx.x (xx.x)	xx.x (xx.x)
Mean (SD) maternal education, years	xx.x (xx.x)	xx.x (xx.x)
Mean (SD) number of children below 5 years of age in the household	xx.x (xx.x)	xx.x (xx.x)

SD = standard deviation; MUAC = mid-upper arm circumference; LAZ = length-for-age Z-score; WLZ = weight-for-length Z-score; BMI = body mass index

Table 2. Primary outcomes

Outcome	Placebo	Azithromycin	RR (95% CI)*	p-value
180 day mortality	n/N (%)	n/N (%)		
ΔLAZ mean (sd)		NA		

* from adjusted generalized linear mixed model

RR = Risk Ratio; CI = confidence interval; ΔLAZ = mean change in length-for-age Z-score

Table 3. Anthropometric parameters

Anthropometric parameter	Placebo	Azithromycin	Effect (95% CI)	P-value
Day 90 anthropometry performed, N (%)				
LAZ at day 90, Mean (sd)				
WAZ at day 90, Mean (sd)				
ΔWAZ (95%CI)				
WLZ at day 90, Mean (sd)				
ΔWLZ (95%CI)				
MUAC at day 90 (cm), Mean (sd)				
ΔMUAC (95%CI)				

Δ = mean change in anthropometric parameter between day 1 and day 90; LAZ = length-for-age Z-score; WAZ = weight-for-age Z-score; WLZ = weight-for-length Z-score; MUAC = mid-upper arm circumference

Table 4. Secondary outcomes

Outcome	Placebo	Azithromycin	RR (95% CI)*	Wald test p-value
Day 10 hospitalization or death	n/N (%)	n/N (%)		
Day 90 hospitalization or death	n/N (%)	n/N (%)		
Day 90 hospitalization	n/N (%)	n/N (%)		

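### Model 6 in SAP 9.3 codes hospitalization to day 180 with no death term, contradicting the three 10- and 90-day endpoints it is meant to analyse

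*SAP*

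**What the plan says.** SAP 3.2 lists the three hospitalization endpoints as secondary objectives 1 to 3. The first is the "proportion of children with at least one hospitalization in the 90 days following enrolment". The second and third add death, over 90 and 10 days respectively. The hypotheses in SAP section 5 follow the same order and windows: "the proportion of children hospitalized by day 90 after enrolment", "the proportion of children hospitalized or dying by D90 after enrolment" and "the proportion of children hospitalized or dying by day 10 after enrolment". SAP 7.4 defines hospitalization as a first episode within 10 days and a first episode within 90 days. SAP 7.1 counts enrolment as Study Day 1, so the death components close on Study Days 11 and 91. Table 4 has one row for each endpoint, for example "Day 90 hospitalization or death".

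The list that opens SAP 9.3 repeats these three endpoints. The section then gives one log-binomial mixed model, Model 6, in which Y=1 means "hospitalized at least once by day 180" and Y=0 means that the child was not admitted. Model 7 keeps this Y and adds covariates. Section 9.3 also says that "date of hospitalization is missing for all events after 10 days of follow-up".

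**The concern.** A prespecified model should analyse the endpoint it is attached to. Here the coding has a window that no hospitalization objective, hypothesis, outcome definition or table row in the SAP uses, and it leaves death out of two endpoints that include it by definition. If the programmer takes Y from the model statement, the result estimates a different quantity from the stated secondary endpoints. One variable would also have to serve three rows of Table 4.

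The missing dates add to the problem. A day-180 flag cannot be cut back to day 90 by date, so the choice of reporting contact that closes the 90-day window has to be made when the variable is built. The SAP does not make that choice.

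**Working it through.** No figure in the plan is at issue, so the check sets the passages side by side and then codes example children under each rule.

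**Step 1: Model 6 against each endpoint** (numbers as in SAP 3.2).

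| Endpoint | Window required | Death included? | Model 6 window | Model 6 death term | Match |
|---|---|---|---|---|---|
| 1. Hospitalization | 90 days | no | 180 days | none | no: window |
| 2. Hospitalization or death | 90 days | yes | 180 days | none | no: window and death |
| 3. Hospitalization or death | 10 days | yes | 180 days | none | no: window and death |

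Matches: 0 of 3. Endpoint 1 rightly has no death term and fails on the window alone.

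**Step 2: example children** (chosen to show the coding, not to suggest frequencies).

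| Child | Model 6 Y | Endpoint 1 | Endpoint 2 | Endpoint 3 |
|---|---|---|---|---|
| First admission day 120, alive | 1 | 0 | 0 | 0 |
| Died at home day 5, never admitted | 0 | 0 | 1 | 1 |
| Died at home day 40, never admitted | 0 | 0 | 1 | 0 |
| First admission day 30 | 1 | 1 | 1 | 0 |

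Model 6 miscodes one of these four children for endpoint 1, three for endpoint 2 and three for endpoint 3.

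**Step 3: can the day-180 rule be run?** Yes. Protocol 6.3 asks at the day-180 contact about admissions since the day-90 visit. Protocol 6.4 and section 7 carry hospitalization data to day 180. A day-180 variable can therefore be built, and it differs from a day-90 variable whenever a first admission falls in between.

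**Step 4: does anything in 9.3 redefine Y?** No. SAP 9.4.1 reuses Models 3 to 5 and says that Y is replaced by each new outcome; 9.3 has no such sentence. Section 9.3 names the first hospitalization per child as the event to be considered, which again leaves out death. Protocol 10.2 lists the three objectives without a model.

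**Step 5: can the window be fixed by date?** Not after day 10, since those dates are missing. Only the contact at which an admission was reported (day 45, day 90 or day 180) separates earlier from later admissions. Protocol 6.2 schedules the day-90 visit between days 80 and 100, but SAP 9.2 expects some visits outside the window and keeps those children in the growth intention-to-treat analysis. A rule based on the visit therefore has no fixed day limit.

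**Step 6: do the objective numbers help?** No. The list in 9.3 runs day-10 composite, day-90 hospitalization, day-90 composite, which is not the order in 3.2. SAP 7.1 refers to "death by day 10 (part of Secondary Outcome 4) and day 90 (part of Secondary Objective 6"), but in 3.2 objectives 4 and 6 are change in WLZ and change in MUAC. The protocol's numbering does not rescue the label either: in Protocol 1.2 the day-10 composite is objective 5 and the day-90 composite is objective 4.

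**The case against.** The strongest reply is that the SAP already settles what is meant. Section 7 is the chapter that defines outcomes. Its 7.4 gives the 10- and 90-day hospitalization windows and their data sources, and 7.1 gives the Study Day 11 and 91 death cut-offs. Sections 3.2 and 5, the list in 9.3 and Table 4 agree with them. An analyst would have to follow one line against all of these and still fill rows labelled day 10 and day 90. On this view the line is a drafting slip.

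Most of that stands. The intended endpoints are recoverable, and much of the repair restates text already in 7.1 and 7.4. Two things remain. The conflicting line is the model's own outcome statement, and it can be run on the data collected. SAP section 11 also treats the statistician's analysis as final and rules out parallel analyses of the same question, so no planned second analysis would expose the mismatch.

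A reader might also infer that day-180 coding must dilute the treatment effect and cost power. The documents do not support this. Later admissions would pull the risk ratio towards 1 if treatment had no effect after day 90. If the effect persisted, they would add events with little change in the ratio. No hospitalization rate, later effect or power target for these endpoints is given, so any figure would rest wholly on assumptions. Nor do the documents say how many children died without an admission; SAP section 2 reports very small numbers of deaths overall, which limits how many composite events could be lost this way.

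**Conclusion.** The point holds as an internal contradiction. The Model 6 outcome, reused in Model 7, has the wrong window for all three hospitalization endpoints and lacks death in the two composites. It should be corrected before these outcomes are coded. The conclusion rests on the text alone and needs no numerical assumption.

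The reach is limited to three secondary endpoints; neither primary outcome is touched. The size and direction of any effect on the risk ratios cannot be determined from the documents. Two stronger readings should not be drawn: that the endpoints are undefined, since 3.2, section 5, 7.1, 7.4 and Table 4 define them consistently, and that the analysis was in fact run to day 180, since the documents contain a plan and no hospitalization results.

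**What to change.** Replace the Model 6 outcome with three definitions, numbered as in SAP 3.2 and tied to 7.1 and 7.4, and state that Models 6 and 7 are fitted once for each:

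1. one or more hospitalizations within 90 days of enrolment;
2. hospitalization within 90 days, or death by Study Day 91;
3. hospitalization within 10 days, or death by Study Day 11.

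Because admission dates are missing after day 10, state that the 90-day hospitalization component uses admissions reported up to and including the day-90 visit, whenever that visit took place, and excludes those reported only at the day-180 contact. Acknowledge that the visit may fall outside days 80 to 100, while deaths are cut at Study Day 91. Report the number of children whose admission cannot be assigned, for example those who missed the day-90 visit but were reached at day 180.

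Align the objective numbers in 7.1 and the list order in 9.3 with 3.2.

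The cost is a short SAP edit and outcome coding from data already collected. Undated admissions around the day-90 visit will stay ambiguous and can only be counted and reported.

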9.4.1 Outcome Definitions

1. Δ WLZ = WLZ at endline visit *minus* WLZ at randomization visit
2. Δ WAZ = WAZ at endline visit *minus* WAZ at randomization visit
3. Δ MUAC = MUAC at endline day visit *minus* MUAC at randomization visit

In sensitivity analysis the endline visit date will be restricted to those who had the visit from study day 91 to 100.

The group means for WLZ, WAZ and MUAC at baseline, endline and mean change will be presented by group as indicated in Table 3. We will use generalized linear mixed models with Δ WLZ, Δ WAZ or Δ MUAC as response variables and treatment group and fixed effects for study country and random effects for clinic and child as the explanatory variables. A sensitivity analyses including potential effect modifiers and unbalanced confounders will be done. Modeling will be analogous to Models 3-5 listed in Section 9.2, but where Y_{ij} is Δ WLZ, Δ WAZ or Δ MUAC respectively, in child i at time j .

9.5 Analysis of Secondary Objective 8 – Antibiotic resistance in enrolled participants

To compare prevalence of azithromycin resistant *E.coli* and azithromycin resistant *S. pneumoniae* respectively in stool and nasopharyngeal swabs submitted for antimicrobial resistance testing at D90 and D180 among a random subsample of enrolled participants, by trial allocation arm.

